5.0 Procedures Involved

5.1 Study Design: This is a double-blind, RCT performed in the University of Minnesota Department of Psychiatry. 235 participants (150 expected to provide complete data) with recent-onset psychosis will be stratified by education and symptom severity and will be randomized into one of three intervention groups: 1) Web-based targeted cognitive training (TCT); 2) Web-based general cognitive exercises focusing on executive dysfunction (GCE); or 3) treatment as usual (TAU). All participants will be asked to participate in a screening/baseline battery ; a 12 week Intervention Phase where they receive computerized training or treatment as usual; a post-intervention follow up assessment battery ; and a 6 month follow-up assessment battery . Total participation will last approximately 36-52 weeks (9-12 months).

5.2 Study Procedures:

For a graphical representation of study procedures, please refer to Section 26 Schedule of Events. Section 6.2 Data contains a full list of the assessments and measures collected in this study.

At any point in the study, unscheduled visits may be used to collect data that was missed during previous appointments (e.g., a visit was cut short; technical difficulties prevented data collection).

For all study timepoints, a limited battery may be delivered remotely; these items have been identified in Section 6.2 Data and Section 25 Schedule of Events. Interviews and cognitive measures will be conducted over Zoom teleconferencing

or by phone, and self-report assessments may be completed via links to a REDCap database sent over email.

Pre-Screening: Potential participants will be provided with information about the study using an established script and will be asked a series of questions to determine if they meet basic inclusion/exclusion criteria. They will be told about the basic aims of the study. Individuals who are interested in participating and appear to qualify for the study will be invited to a consent discussion (see Section 22 Consent Procedures).

Screening/Baseline Assessments (1-4 weeks): After the participant has provided informed consent, we will begin conducting the screening assessments to determine their eligibility to participate in the study. Eligibility to participate will be determined through use of the MINI and/or a review of recent medical history, including medications. Participants may complete intake interviews while waiting to achieve clinical stability in medication regimen (recent changes to medication are permissible). The suicidality module of the MINI will not be used to assess suicidality risk; instead, the C-SSRS will be used at screening to determine past behavior and current risk. If a C-SSRS is not conclusive towards the suicidality risk of a participant, study staff may consult with the participant's clinician to determine whether they are clinically stable enough to participate in the study. This determination will be documented as a Note to File within the participant's record. A SCID may be conducted in more complex cases where a MINI does not deliver a clear diagnosis. Other eligibility assessments include the demographics, WTAR, and Substance Use Summary forms. If the participant qualifies to participate in the study, Baseline evaluations will begin.

Participants must be clinically stable before beginning baseline assessments, defined as no hospitalizations or significant changes to medication regimens for a minimum 30 days. The PI will make case by case determinations as to whether a change in medication constitutes a significant change. Baseline assessments will evaluate neurocognition, social cognition, clinical symptoms, and functional status, as well as computer, video game and internet usage. For a list of the assessments used, please refer to Section 6.2 Data and Section 26 Schedule of Events.

Total baseline assessment time for neurocognition, clinical symptoms, functional status, and user ratings will be approximately 7 hours spread over 1-4 appointments in a 1-4 week period. Participants who are placed on a hold due to medication changes or hospitalizations will have 1 to 4 weeks to complete the baseline assessments once they re-enter the study.

If participants provide their consent for the interviews to be videotaped or audio recorded, a video camera will be set up to record the participant during their diagnostic and/or clinical interview. For in person visits, a camera will be

PROTOCOL TITLE: Minneapolis Community-Based Cognitive Training in Early Psychosis (Mini-COTES)
VERSION 10.0 21 April 2020

positioned so the participant's face and body are visible to capture affective changes and motor behaviors. If the participant only provides permission for audio recording, the camera will still record, but the viewfinder will be closed. Interviews will not be recorded during remote visits. Please refer to Section 6.0 Data Banking for clarification on how video data will be stored.

After baseline measurements have been completed, the participant will be randomized to one of the three study arms.

Intervention Phase (6-12 weeks): For participants who are randomized to TCT or GCE, we will ask them to complete 60 minutes of training 5 times a week (5 hours per week) over the course of 6 weeks for a total of 30 hours of training. Though we will encourage participants to complete the training within a 6 week period, we will allow them up to 12 weeks to complete the training protocol. iPads loaned to participants may be delivered via the mail. Prior to mailing, staff will follow the manufacturer's guidelines to disinfect the iPads using a 70 percent isopropyl alcohol wipe or Clorox Disinfecting Wipes. Study participants randomized to the cognitive training conditions will maintain weekly contact with study staff by telephone, text, and/or email to check in on their training progress, to see if they have had any adverse events, and to ensure that they wish to remain in the study.

Study participants who are randomized to TAU will not be regularly contacted by study staff until it is time to schedule their Post-Intervention Assessments (12 weeks post Baseline). Participants will be asked to contact study staff if they have any adverse events, such as hospitalization; however, this will be reviewed when scheduling the participant for their next visit. Study staff may contact participants during the 12 week period as needed to inform them of changes to the project or to keep them engaged in the study.

For a description of the training programs, please refer to Section 4.

Post-Intervention Assessments (1-4 weeks): After the participants have completed the Intervention Phase, they will be invited to participate in post-intervention assessments. Their appointments will be scheduled after completing the training program, notifying study staff that they no longer wish to participate in training, or after 12 weeks have passed since the Baseline Assessments were completed. The Post-Intervention Assessments should last approximately 5 hours and may be split up into 1-4 visits across 1-4 weeks. We will repeat the baseline measurements in neurocognition, social cognition, clinical symptoms, and functional status, as well as Resource Utilization and Substance Use summary forms. If participants have consented to audio or video recording, their clinical interview will be recorded following the procedures described above.

PROTOCOL TITLE: Minneapolis Community-Based Cognitive Training in Early Psychosis (Mini-COTES)
VERSION 10.0 21 April 2020

In addition to repeating baseline measures, we will measure the feasibility and acceptability of the cognitive training programs through 1) attrition rates; 2) time to completion of training; 3) user and clinician ratings of acceptability.

Participants who completed training will be asked to complete a 22-item, Likert-type questionnaire composed of elements of a measure used previously by Posit Science to evaluate acceptability for their cognitive training software, and components of a measure we have used previously to assess acceptability of training in our recent-onset RCT. Items assess user experience and satisfaction with the programs, the web-based administration, and the training schedule. We will also collect this data from their treating clinician in the First Episode Psychosis clinic. These questionnaires may be completed in-person or collected remotely using REDCap. For participants who are lost to follow up and are unable to provide this data, study staff will complete the Participant Closeout Report to provide some final data on their participation in their case records.

If participants were loaned an iPad and/or other devices to complete study activities at home and no longer wish to participate in study activities, including their post-intervention interviews, study staff will attempt to coordinate with the participant to meet them before or after a regularly scheduled clinic appointment to return the device(s). If the participant is no longer receiving care at the UMP Psychiatry Clinics, if in-person appointments are not available, or if they cannot be reached, study staff will send them a letter asking them to return the devices along with a box with a return label. Participants will be invited to come back for their post-intervention visit in this letter, but also reminded that they are free to no longer participate in the study.

6 Month Follow-Up: Participants will enter the follow up period after the completion of their Post-Intervention Assessments. We will ask them to refrain from participating in any other research studies or completing other commercially available cognitive training programs during this time to avoid confounding our results. We will inform them that if they wish to participate in another study or complete a different cognitive training program they may do so, but we would withdraw them from this study at that time.

Study staff may contact participants during the six-month follow up period as needed to inform them of changes to the project or to keep them engaged in the research. Participants will be contacted 2-4 weeks before their approximate 6 month follow-up date to verify that they wish to continue participating and to schedule their appointment. We will repeat the baseline measurements in neurocognition, social cognition, clinical symptoms, and functional status, as well

PROTOCOL TITLE: Minneapolis Community-Based Cognitive Training in Early Psychosis (Mini-COTES)
VERSION 10.0 21 April 2020

as Resource Utilization and Substance Use Summary forms. If participants have consented to audio or video recording, their clinical interview will be recorded following the procedures described above. The batteries should last approximately 5 hours and may be split up into 1-4 visits across 1-4 weeks. Upon completion, the participant will have completed the study. Participants who were randomized to the TAU arm will now be offered access to either of the computerized training programs.

COVID19 Procedures

Due to social distancing requirements during the COVID19 outbreak, participants will not be able to attend in-person visits. To accommodate for this situation, participants will be asked to complete remote assessments using a limited battery, which is identified in Section 6.2 Data and Section 26 Schedule of Events. Any missing data from in-person assessments may be collected later once social distancing procedures are lifted, at PI discretion.

To further accommodate participants' needs, the timeframes during which study activities can be completed will be extended while social distancing procedures are in place. These accommodations will be temporary; when social distancing procedures are lifted, study timeframes will return to the windows described above. At this time, the PI will make case-by-case determinations as to whether participants will be expected to adhere to the standard timeframes or the COVID19 timeframes for their current event window.

The adjusted timeframes are as follows:

- Screening/Baseline: 1-6 weeks
- Intervention Period: 6-16 weeks
- Post-Intervention Assessment: 1-6 weeks
- 6 Month Follow-Up Assessment: 1-6 weeks
- Total duration of study activities: 35-60 weeks (8-15 months)

However, if participants need additional time due to illness, caring for loved ones who are ill, or other extenuating circumstances related to COVID19, they will be provided additional support and time to complete the assessment battery, at PI discretion.

5.3 Individually Identifiable Health Information:

Participation in this study will involve collection of individually identifiable information. This includes:

- Full name
- Contact information: Phone number, email address, mailing address
- Date of Birth

- Medical Record Number
- Study staff may review the participant's Electronic Medical Record (EMR) to confirm appointment scheduling, medication lists, diagnostic information, and for review of treatment services utilized during the study. In the case of significant medical events (e.g., traumatic brain injury), study staff may review the EMR or request records from their treating clinicians to provide context for study data.
- If a participant is going to earn over \$600 in a calendar year for study compensation, we will require the participant's Social Security Number to report their earnings to the IRS.
- Participants will be asked to provide consent for videotaping or audio recording of their clinical assessments

For further details about the storage of PHI, please refer to the following sections: 6.0 Data Banking; 12.5 Payment; 17.0 Data Management; 20.0 Provisions to Protect the Privacy Interests of Participants.

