3.0 Study Specific Aims

3.1 Specific Aims:

1. Perform a double-blind RCT of web-based, portable computerized cognitive training in young individuals with recent onset psychosis receiving treatment within the University of Minnesota, Department of Psychiatry's First Episode Psychosis Program or other state clinics utilizing the NAVIGATE treatment model.
2. Compare the clinical and cognitive effects of neural system-informed TCT that focuses explicitly and specifically on distributed neural system efficiency in auditory/verbal and social cognitive domains, vs. more non-specific GCE designed to enhance executive functioning and problem-solving, vs. TAU. Determine the durability of these effects and their relationship to functional outcome over a 6 month period.

3. As a secondary aim, investigate the feasibility, tolerability, and acceptability of the intervention by service providers, clients, and caregivers in these real-world treatment centers.

3.2 Hypotheses to be tested:

1. TCT participants will show significantly greater gains in general cognition, verbal learning/memory, and social cognition compared to GCE and TAU participants. These gains in the TCT group will be sustained at 6-month follow-up.
2. GCE participants will show improvement in problem-solving and global cognition compared to TAU participants. At 6 month follow-up, GCE participants will show lower gains in global cognition and verbal learning/memory than TCT participants.
3. Gains in general cognition and processing speed, and in social cognition in TCT participants will correlate with improvements on 6-month measures of occupational and social functioning, respectively, as well as internalized stigma. These associations will be significantly greater in TCT participants vs. GCE or TAU participants.
4. Symptom ratings will show improvement in all participant groups at 6 months, with no significant between-group differences.
5. At least 70% of randomized clients will complete >20 hours of training in the TCT and GCE arms.
6. Participants and clinicians will rate the TCT and GCE interventions as equally feasible, tolerable, and acceptable.

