4.0 Study Intervention(s)/Interaction(s)

4.1 Intervention: This protocol examines the effects of two modes of remote cognitive training compared to regular clinical care over a period of 6-12 weeks. Participants will be randomized to one of three conditions: Targeted Cognitive Training, General Cognitive Exercises, or Treatment as Usual.

Participants randomized to one of the two training conditions will be asked to complete 60 minutes of training 5 times per week over the course of 6 weeks for a total of 30 hours of training. They will be loaned an iPad to complete their training sessions remotely at home, or they may come to the Department of Psychiatry to complete their training. Participants who have their own device may use their own iPad to complete training if they wish; however, they will still be offered the use of a UMN iPad for their training. Though we will encourage participants to complete

the training within a 6 week period, we will allow them up to 12 weeks to complete the training protocol.

Participants randomized to the treatment as usual condition will continue receiving their standard care from the First Episode Psychosis Program or a clinic utilizing the NAVIGATE model. After they complete their final assessment, participants in the treatment as usual group will be offered access to the training program of their choice, if they would like to complete the training.

Assessments will be conducted at Baseline, End of Intervention/12 weeks, and after a 6 month follow up to determine the effects of training on symptoms, behaviors, cognition, and social cognition.

4.2 Targeted Cognitive Training (TCT): The TCT program will be provided by Posit Science free of charge and will consist of a set of iPad application-based exercises in two components: an auditory/verbal processing training module which will be applied for 20 hours, and a social cognition training module which will be applied for 10 hours. Compliance is monitored by data upload following each training session.

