Participants who are randomized to this arm of the study will be offered access to the program of their choice after the completion of their 6 month follow up visit.

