14.0 Risks to Participants

14.1 Foreseeable Risks:

- Risks of Assessments and Batteries: As with all assessments, there is the potential that we will ask questions that make the participant feel uncomfortable, embarrassed, or stressed. We will remind participants that they only need to provide the information that they are willing to answer and can ask to skip questions at any time. In addition, due to the length of the assessment visits, it is possible that participants can feel fatigued or stressed by the interview. We provide the option to split the assessment batteries over several visits in 1-4 week period to reduce the burden on the participant, and

PROTOCOL TITLE: Minneapolis Community-Based Cognitive Training in Early

Psychosis (Mini-COTES)

VERSION 10.0 21 April 2020

we will invite them to take short breaks in the middle of sessions to prevent fatigue. Refreshments may be offered during longer appointment sessions.

- Risks of Computerized Training: Participants may become frustrated or fatigued when participating in their computerized training program. To mitigate these risks, we remind participants that they should only complete 60 minutes of training per day, 5 days a week to prevent them from feeling overburdened. Additionally, they may take breaks in their training sessions if they need to. The programs are self-adaptive to adjust difficulty level to approximately 80% success rates for individuals, which should help prevent feelings of frustration during the training programs.
- Randomization Risks: Since participants are randomly assigned to their intervention arm, they may receive an intervention that is less effective or has more side effects than the other study interventions, or other available treatments. There is also the chance that they will not receive any cognitive training at all during their participation in this study. However, the risks of randomization are not greater than minimal risk.
- Confidentiality Risks: Participation in research will involve a loss of privacy due to the data collected during training sessions. However, records will be handled as confidentially as possible. Please refer to sections 6.0 Data Banking, 16.0 Data Management, and 17.0 Confidentiality for further information about how PHI is handled in this study.

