19.2 Data Safety Monitoring

This is a minimal risk trial and we do not anticipate any adverse events from participation in the study. Nonetheless, to follow best practices for clinical research, we will follow the Participant Safety Monitoring Plan outlined below to review Unanticipated Problems and Adverse Events.

[name] Lab Participant Safety Monitoring Plan

Participants will be screened for eligibility according to the procedures described in Section 8.3 Screening to avoid unnecessary exposure to risk.

Study Coordinators and Clinical Assessors will have regular contact with research participants described in Section 5.2 Study Procedures. Participant safety will be monitored using assessments defined in Sections 5.2 Study Procedures and 6.2 Data. Study Coordinators and Clinical Assessors will be trained by [name] Lab Management to recognize symptoms that indicate worsening clinical status, suicidal and homicidal ideation, self-harm, and abuse or neglect.

Study Coordinators will deliver regular participant updates to the PI and Co-Is at the weekly [name] Lab Meeting and other team meetings. In the case where a Study Coordinator misses a team meeting, they will coordinate with their supervisor or an Investigator to deliver participant updates.

If a Study Coordinator or a Clinical Assessor becomes aware of a significant change in functioning or behavior, or if they are concerned for the welfare of the participant or others, they will report their findings to an Investigator as soon as possible. If there is an immediate safety concern, the Investigator will initiate the Crisis Protocol. If there is no immediate concern, the case will be discussed with the PI at the next meeting. The Investigators will follow the procedures outlined in Section 12.0 Withdrawal of Participants and Section 21.6 Cognitively Impaired Adults, as applicable.

If the Study Coordinators or Clinical Assessors learn of potential or confirmed abuse or neglect of a child or a vulnerable adult, the Investigators will consult with the University of Minnesota Office of General Counsel to determine whether they need to follow Mandated Reporting procedures.

Unanticipated Problems, Adverse Events, and follow up will be documented via Notes to File signed by the PI and stored in the participant's record in Box. The PI will determine whether the event needs to be reported to the IRB, per the HRP-103 Investigator Manual.

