2: TCT/GCE participants will be encouraged to complete the training in 6 weeks if possible, but will be allowed up to 12 weeks to complete the 30 hours of training. All TAU participants will be followed for 12 weeks.

3: The SCID will only be conducted in complex cases when the MINI will not be sufficient to determine the participant's diagnosis

4: The review of medical records and medication lists will occur within +/-5 days of the scheduled visit.

5: Resource Utilization Survey will be captured at baseline, post-training, and 6-month follow-up. Study staff will use medical records, information from providers, and participant self-report.

6: If the participant disengages from clinical services and is unable to complete the post-training survey, study staff will complete the participant closeout report

7: Participants in the TCT/GCE arm will be asked to complete 5 60 minute sessions of cognitive training per week.

8: During the Intervention phase, the phone check in will be weekly for TCT and GCE participants to update them on training status. Participants randomized to TAU will not be contacted.

9: If there is a period of more than 2 weeks between the 2 appointments at each period (e.g., V1 & V2), the COVID19 Stress Screener will be re-administered at the second appointment.

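### The whole three-arm trial is labelled double-blind, but TAU participants know their arm, so neither contrast with TAU can be participant-blind; rater masking is not described

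*Combined protocol and SAP*

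**What the plan says.** The label is unqualified. Section 5.1 reads "This is a double-blind, RCT performed in the University of Minnesota Department of Psychiatry", and the first aim in Section 3.1, repeated in the Study Summary, is to "Perform a double-blind RCT of web-based, portable computerized cognitive training in young individuals with recent onset psychosis". None of these places says who is masked or by what means.

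The third arm is described differently. Section 4.1: "Participants randomized to the treatment as usual condition will continue receiving their standard care". Section 14.1 lists as a randomization risk: "There is also the chance that they will not receive any cognitive training at all during their participation in this study". Section 4.4: "Participants who are randomized to this arm of the study will be offered access to the program of their choice after the completion of their" 6-month visit. Section 26, note 8, on the intervention phase: "Participants randomized to TAU will not be contacted". Section 5.2 is a little looser, since it rules out regular contact but allows contact as needed. The training arms get weekly check-ins about training progress (Section 5.2) and payment per five hours trained (Section 12.5).

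On assessors, Section 19.2 says: "Study Coordinators and Clinical Assessors will have regular contact with research participants"; that sentence goes on to refer to the contact set out in Section 5.2. On the post-intervention assessment, Section 5.2 says: "Participants who completed training will be asked to complete a 22-item, Likert-type questionnaire".

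**The concern.** A double-blind label tells the reader that neither expectation nor knowledge of allocation could have shaped the outcomes. For contrasts with TAU that is untrue on the participant side, and the plan does not show it to be true on the rater side.

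The TAU contrasts carry stated conclusions. Section 4.4 uses TAU to decide whether changes in symptoms, cognition and functioning are due to training or to clinic care. Hypothesis 4 compares symptom ratings across all three groups. Hypothesis 3 compares associations with functioning and internalized stigma in TCT against those in GCE or TAU. These draw on interview and self-report scales such as PANSS, QLS, SFS, Global Functioning and ISMI. A participant who knows that training was withheld, or a rater who knows it, can shift such scores in either direction. A report calling these contrasts double-blind would overstate the evidence.

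**Working it through.** The plan states no figure for masking, so the check is mainly a comparison of sections.

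**Participants**
- TCT and GCE are both adaptive exercise programs from the same supplier (Sections 4.2 and 4.3). Participant masking between these two is plausible, although not described.
- TAU has no program and no sham (Sections 4.1 and 4.4), no weekly check-in (Section 5.2; Section 26, note 8) and no training payments (Section 12.5). Participants know that a no-training outcome exists (Section 14.1), and TAU participants are offered a program only after the 6-month visit (Section 4.4).
- Of the three pairwise contrasts (TCT–GCE, TCT–TAU, GCE–TAU), the two involving TAU cannot be participant-blind. This follows from the design alone.

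**Raters**

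No section states that assessors are masked. Four features could reveal the arm:
1. *Training survey.* It goes only to participants who completed training. PANSS, QLS, GAF-M and Global Functioning are at V3 in Section 26. The survey appears to line up with V4, although the column alignment cannot be read with certainty. Note 1 allows V3 and V4 in either order, so nothing ensures that ratings come first.
2. *Visit timing.* Training participants are assessed on finishing or stopping training, or at 12 weeks (Section 5.2). All TAU participants are followed for 12 weeks (Section 26, note 2). An earlier visit therefore points to a training arm.
3. *Contact.* It differs by arm, and Section 19.2 names assessors together with coordinators as having the Section 5.2 contact.
4. *Rating checks.* Study staff review recordings, with no masking stated (Section 17.3). Remote interviews are not recorded (Section 5.2), so masked re-rating is not available for them.

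**Which hypotheses are exposed**
- Hypotheses 1 and 2 use cognitive composites, mainly performance tests (Section 17.1). They are less exposed, though not immune.
- Hypotheses 3 and 4 and the Section 4.4 aim involve the interview and self-report scales.

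**Illustration of size (the bias is assumed)**

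Take 50 per arm (Sections 4.4 and 17.2), no true effect, and a two-sided 0.05 test of two means. In SD units the standard error is √(2/50) = 0.2, so a bias of b SD moves the test statistic by b/0.2 = 5b. The rejection probability is 1 − Φ(1.96 − 5b) + Φ(−1.96 − 5b).

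| Assumed bias b (SD) | 5b | Normal approximation | Noncentral t |
|---|---|---|---|
| 0.1 | 0.5 | 7.9% | 7.9% |
| 0.2 | 1.0 | 17.0% | 16.8% |
| 0.3 | 1.5 | 32.3% | 31.8% |

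These figures describe a simple two-arm mean contrast. They do not describe Hypothesis 3, which compares Pearson correlations of change scores: a constant shift within an arm leaves that arm's correlation unchanged. Nor do they describe Hypothesis 4, which uses a three-group repeated-measures ANOVA and predicts no difference.

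**The case against.** The best defence is that the label was meant for the main comparison. Section 2.1 ties the double-blind design to TCT vs GCE, Section 17.2 powers only that contrast, and Section 14.1 says openly that some participants will get no training. This stands as a reason to rescope the label rather than doubt the powered comparison. It does not rescue the wording in Sections 3.1 and 5.1 and the Study Summary, which covers all three arms.

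A reader might infer that raters are in fact unblinded. The documents do not support that. Section 5.2 assigns the weekly check-ins to study staff without naming assessors, and the contact mentioned in Section 19.2 includes the assessment visits themselves. Section 24.4 gives assessors and coordinators separate meetings with different agendas. The survey seems to sit at a different visit from the main ratings and may be completed remotely. No text says that assessors run check-ins or are told the arm. What remains is that allocation could be revealed and no stated safeguard prevents it.

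A reader might also take 8%, 17% and 32% as error rates for Hypotheses 3 and 4. They are not, for the reasons shown in the working. Under Hypothesis 4 a spurious difference would count against the prediction, while bias could equally hide a real difference.

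**Conclusion.** The point holds on the participant side without any assumption: two of three contrasts lack a property that the plan claims for the whole trial. On the rater side the finding is one of silence: masking is not described, and routes to unmasking exist but are not shown to operate. The contrasts most affected are those with TAU on self-report and interview scales.

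The size of any bias is unknown. The rise from 5% to about 8%, 17% or 32% is conditional on an assumed bias of 0.1, 0.2 or 0.3 SD, 50 analysed per arm and a two-arm comparison of means. It shows only that a modest shift would matter.

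Two stronger conclusions are not warranted. TCT vs GCE is not shown to be compromised. Nor do the TAU contrasts on these scales need to be dropped, since that would give up the symptom and functional part of the Section 4.4 aim; they need accurate labelling.

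**What to change.** 1. In the Study Summary and Sections 3.1 and 5.1, limit any double-blind claim to TCT vs GCE and describe TAU as open to participants.
2. State whether the raters of PANSS, QLS, GAF-M and Global Functioning are masked, and how. The double-blind wording for TCT vs GCE should depend on that answer.
3. Report TAU contrasts on self-report and interview scales as participant-unblinded, and as rater-unblinded too unless rater masking is in place. Keep these contrasts in the analysis.
4. Send the post-training survey by REDCap, which Section 5.2 already allows, only after that participant's ratings are complete.
5. Have existing staff who do not run a participant's weekly check-ins carry out that participant's ratings.

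The cost is protocol wording, the order of one survey, a small scheduling constraint among existing staff, and a less favourable design label. No new arm, measure or sample is needed.
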